APPENDIX B SEIZURE CLASSIFICATION AND SUBJECT DIARY

Seizure Classification

At the Baseline visit, the investigator or authorized delegate will collect seizure information from the subject and/or caregiver. Information about each seizure type will be collected on a *Seizure Classification - Initial* CRF. Based upon the definition provided by the subject/caregiver, the investigator will classify the seizure based on the International League Against Epilepsy (ILAE) definitions (see Table 4). As subjects may experience multiple kinds of seizures within one class (e.g., two kinds of simple partial seizures), each seizure will be assigned a *seizure letter*. Seizure letters will be assigned alphabetically starting with A.

**Table 4: Seizure Classification
(International League Against Epilepsy)**

Focal Seizures
Without impairment of consciousness or responsiveness
With observable motor or autonomic components
Involving subjective sensory or psychic phenomena only
With impairment of consciousness or responsiveness
Evolving to a bilateral, convulsive seizure
Generalized Seizures
Absence
Typical
Atypical
Myoclonic absence
Eyelid myoclonia
Myoclonic
Myoclonic
Myoclonic atonic
Myoclonic tonic
Tonic
Clonic
Tonic clonic
Atonic
Unclassified Seizures
Epileptic spasms – focal or generalized
Seizure type is unclassified

If at any time during the study the subject experiences a new type of seizure, a new *Seizure Classification - Initial Report* CRF and an *Adverse Event* CRF will be completed. A *Seizure Classification - Update* CRF will be completed if there are any *changes* to previously reported seizure types. At a minimum, the *Seizure Classification - Update* CRF will be completed for each seizure type at the Month 3, Month 6, and Month 12 visits.

Retrospective Seizure Data Collection

Retrospective seizure frequency data will be collected at the Baseline visit. Retrospective reporting will be based on the subject's seizure history and, if available, a subject diary. Although 3 months of seizure frequency data is needed to determine eligibility, seizure count data for the 12 months prior to baseline will be collected, if available.

Diary

The Sponsor will provide a standard diary on which the subject and/or caregiver can record seizure activity. Each diary contains the following information:

- A "key" to the seizure types correlating the assigned seizure letter to the subject's usual descriptor of the seizure (e.g., Seizure Type A = the "big one")
- A calendar to record daily seizure activity and missed AED doses
- Other relevant information (e.g., new type of seizure)

Subjects may prefer to use their own diary format (paper or electronic); these will be allowed as long as the subject's diary collects the information listed above.

Subjects may also use the diary to record the following (although this information may be elicited by direct questioning of the subject during a study visit):

- Changes to epilepsy and non-epilepsy medications
- Use of rescue medications
- Recording of non-study-related visits to the doctor, hospital or emergency room.
- Comments section to record other relevant information (e.g., new type of seizure)

Instruction for Diary Completion

At the Baseline visit, and again prior to discharge, the investigator or authorized delegate will instruct the subject/caregiver on proper diary completion. This instruction will include:

- Importance of accurate diary-keeping
- Explanation of the seizure classification key
- How to complete the diary:
 - Recording of seizure activity
 - If no seizures occurred on that day, the subject will be instructed to tick the "no seizure" box for that day
 - If subject missed any dose(s) of their epilepsy medications, the subject will be instructed to tick the "missed epilepsy dose" box for that day
 - Explanation that the NAV (not available) designation on a calendar day is for investigator use only
 - How to record medication changes and use of rescue medications
 - How to record non-study-related visits to the doctor, hospital or emergency room
 - What might be recorded in the "other" section

Recording Seizures

Subjects or their caregiver will keep a seizure diary starting the day after discharge. A new diary is provided at subsequent appointments. The subject or caregiver will record the number and type of seizures each day.

Sites will be instructed to take measures to ensure that diary entries are faithfully recorded in order to minimize missing diary data. Subjects will be trained on the importance of accurate diary-keeping.

At each visit the investigative staff will review the diary with the subject and/or caregiver and address any concerns with diary completion. If seizure information is not available for a specific diary day, the coordinator will tick the “NAV” box for that day. An example of a diary day is shown below.

Sun _____	 NAV
 Missed epilepsy dose	
 No seizures	

Diary Compliance

In order to minimize missing diary data, sites will be instructed to take measures to ensure that diary entries are faithfully recorded. At each visit the investigative staff will review the diary with the subject and/or caregiver and address any concerns with diary completion. The investigator will also provide additional training to new caregivers over the course of the trial, as needed.

Diary Data

The seizure information collected on the diaries will be recorded on a *Diary Summary* CRF. Any additional information recorded on the diary (e.g., about changes in the subject's epilepsy medications, the use of rescue medications, and adverse events) will also be recorded on the applicable CRFs.

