6.3.1 Study Inclusion Criteria

Subjects must meet all of the following inclusion criteria:

1. Diagnosis of unilateral medial temporal lobe epilepsy (MTLE) confirmed clinically and with either (1) ictal scalp recording and MRI evidence of mesial temporal sclerosis or (2) intracranial ictal onset consistent with hippocampal origin
2. Subject's seizures are distinct, stereotypical events that can be reliably counted.
3. Based on medical record, history of an average of at least 1 complex partial or secondarily generalized seizure compatible with MTLE per month for a minimum of the last 12 months prior to the Baseline visit (i.e., at least 12 qualifying seizures in the 12 months prior to the Baseline visit). *(Seizures occurring during inpatient assessment in an epilepsy monitoring unit should not be included in the average).*
4. Subject is on stable antiepileptic drugs (AEDs) for 30 days prior to the Baseline visit and compliant with medication use (as reported by the subject). Stable is defined as no new or discontinued AEDs and no changes to AED total daily dose. *(Exception: (1) temporary changes or discontinuation of AEDs for the purposes of diagnostic or medical procedures during the 30 days preceding the Baseline visit and (2) acute, intermittent use of benzodiazepines or other rescue medications.)*
5. Subject has met the criteria for a medial temporal lobe resection based on the Site's standardized pre-surgical evaluation.
6. Subject is deemed a LITT candidate by the center's epilepsy evaluation team.
7. Subject is 18 years or older at the time of consent.
8. Subject can be reasonably expected to maintain a seizure diary alone or with the assistance of a caregiver.
9. If female, must be postmenopausal, surgically sterile, or, if of childbearing potential, have a serum pregnancy test with a negative result at the Baseline visit and practicing effective contraception.³
10. Subject or legally authorized representative is able to provide appropriate consent to participate.
11. Subject is able to complete regular office and telephone appointments per the protocol requirements.
12. Subject speaks English or Spanish as a primary language. If Spanish, the Site must be able to provide a translated (IRB-approved) consent form and the Site's neuropsychologist must be willing and able to assess the subject in Spanish.

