7.6 Procedures and Subject Assessments

7.6.1 Baseline Visit

Prior to consenting patients for the study, Site personnel will evaluate potential candidates by reviewing the patient medical records against the study eligibility criteria. It is expected that the medical records will contain adequate information to determine if the patient meets these criteria. Potential patients will be asked to complete the informed consent process.

The following evaluations and assessments will be performed at this visit:

- Demographics
- Medical, surgical and epilepsy history
 - Epilepsy history will include collection of 12 months of retrospective seizure frequency data; data from the 3 months prior to the Baseline visit will be used for eligibility determination. See Appendix B for more details.
- Quality of Life in Epilepsy - 31 (QOLIE-31). It is preferred that the subject completes the questionnaire prior to any other baseline tests.
- Medication review, including collection of 12 months of retrospective epilepsy medication data (as available) to qualitatively assess medication stability prior to the NeuroBlate procedure. See Appendix A for more details.
- Physical exam
- Neurological exam
- Visual field testing (automated perimetry)
- Serum pregnancy test (if female and of childbearing potential)
- Neuropsychological testing (see Appendix C).
- Functional assessment (including employment status, education, living arrangements, driving status)
- Seizure classification assessment
- Seizure diary training

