7.6.3 Discharge Visit

Prior to hospital discharge the following evaluations and assessments will be performed:

- Medication review (see Appendix A)
- Physical exam
- Neurological exam
- Adverse event monitoring
- MRI (the MRI performed at the end of the LITT procedure can be used as the Discharge Visit MRI).
- Surgical pain visual analog scale (VAS)
- Seizure diary training refresher and dispensing (see Appendix B)

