10.1.3 Secondary Endpoint: Analysis of Seizure Outcomes

Seizure frequency will be characterized by calculating the rate of seizure occurrence within specific follow-up time periods (count of reported events/reported time frame). Follow-up time periods of interest include all follow-up and between-visit follow-up periods (e.g., procedure to Month 3) to characterize the longitudinal course of seizure frequency. For each time period, descriptive statistics of subject-specific rates characterize the distribution of observed seizure rates. The change from baseline in seizure rates may also be calculated by calculating the difference in rates between a follow-up period and the baseline rate of seizures occurring prior to treatment (count of reported events/reported time frame). Since subjects may have different baseline seizure rates, the relative reduction (follow-up rate/baseline rate - 1) will also be calculated to scale the degree of improvement relative to the baseline rate. These analyses may be repeated for subsets of seizures with specific classifications to characterize the frequency of different seizure types.

The main analysis of seizure frequency will include subjects with at least 70 completed diary days in each 3-month period from procedure through 12 months and at least 140 diary days in each 6-month period from 12 months through study completion. To account for incomplete diary completion, sensitivity analyses may be performed by including subjects with less than the required level of diary completion and by using the number of days with completed diary entries to determine the denominator in the event rate calculation.

Seizure frequency may be further characterized by calculating the proportion of responders. A responder is a subject whose seizure frequency in a specified 3-month interval is reduced by $\geq 50\%$ as compared to baseline.

Seizure free days may be further characterized by calculating the number of seizure-free days that subjects experience during a specified 3-month interval. In order to make the 3-month

follow-up intervals comparable, the number of days actually recorded will be prorated to an 84-day intervals.

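### Rev B sets a mixed-source retrospective seizure baseline against a diary that starts only after discharge, plans no check, and leaves the SAP relying on a baseline diary that is no longer collected

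*Protocol*

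**What the plan says.** Protocol Section 7.6.1 lists "Seizure diary training" among the Baseline visit activities, and Table 1 marks the diary there as training only. Section 7.6.3 places the first dispensing at discharge. Appendix B agrees: "At the Baseline visit, and again prior to discharge, the investigator or authorized delegate will instruct the subject/caregiver on proper diary completion", and then "Subjects or their caregiver will keep a seizure diary starting the day after discharge". Section 7.1 puts LITT within 30 days of the Baseline visit, and the first footnote to Table 1 allows longer where neuropsychological scheduling needs it. No study instrument is assigned to count seizures in that gap.

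Baseline counts are taken once, at the Baseline visit. Appendix B explains: "Retrospective reporting will be based on the subject's seizure history and, if available, a subject diary"; and "seizure count data for the 12 months prior to baseline will be collected, if available". Entry (Section 6.3.1, inclusion 3) rests on the medical record and requires "at least 12 qualifying seizures in the 12 months prior to the Baseline visit".

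Protocol Section 10.1.3 then compares each follow-up rate with "the baseline rate of seizures occurring prior to treatment". It names neither the period nor the source of that baseline. Its measurement-related sensitivity analyses concern incomplete follow-up diaries only.

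The SAP is dated 11 August 2017 and cites protocol Rev A; the current protocol is Rev B, dated November 6, 2017. SAP Table 1 dispenses a diary at Week -12 and collects it through Week 0. SAP Section 11.1.3 defines responders against a three-month Baseline Phase, prorates recorded baseline days to 84, and calculates a longest seizure-free interval for the baseline period.

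**The concern.** The numerator of each percent reduction is a prospective daily diary that staff review with the subject. The denominator is a one-time retrospective count whose source differs from subject to subject. If the two methods capture different shares of the seizures that occur, the ratio combines the effect of LITT with the change of method. There is no control arm in which that change would cancel out.

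The exposed outcomes are the rate change, the relative reduction, the responder proportion, Engel III versus IV (SAP Section 11.1.3 sets worthwhile improvement at a 50% reduction from baseline) and the ILAE 4 to 6 boundaries, which are percentages of baseline seizure days. The ILAE footnote defines those days over the 12 months before surgery, so the uncounted weeks between Baseline and LITT fall inside its window.

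The SAP also specifies analyses that need daily pre-LITT records from every subject, which Rev B does not require. The sample size sections say the results will inform a larger pivotal trial, so an unexamined baseline error could carry into that design.

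**Working it through.** **The plan's own figure.** The documents give no number for baseline capture. Their only sample-size figure is an approximately 80% chance of seeing at least one adverse event of 5% per-subject probability in 30 subjects: 1 - 0.95^30 = 0.785, which reproduces. It does not depend on the seizure baseline.

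**Effect of unequal capture.** Let k be the retrospective baseline count divided by the count a diary would have given over the same period. No document gives k, so the values below are assumptions.

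Reported reduction = 1 - (1 - true reduction)/k. A reported 50% cut corresponds to a true reduction of 1 - 0.5k.

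| k | True 50% reads as | True 90% reads as | True reduction at the 50% responder cut |
|---|---|---|---|
| 0.7 | 1 - 0.5/0.7 = 29% | 1 - 0.1/0.7 = 86% | 65% |
| 0.9 | 1 - 0.5/0.9 = 44% | 1 - 0.1/0.9 = 89% | 55% |
| 1.2 | 1 - 0.5/1.2 = 58% | 1 - 0.1/1.2 = 92% | 40% |

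A true 100% reduction reads as 100% for any k.

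**What a pre-LITT diary could show.** Inputs: 30 subjects; 30 diary days each (the Section 7.1 limit, taken as an assumption); 1 seizure per month (the entry floor) or 3 per month (assumed); a 30.4-day month; Poisson counts; 12 months of retrospective data.

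- At 1 per month: 30 x 30/30.4 = 29.6 diary seizures against 30 x 12 = 360 retrospective. SE of the log ratio = sqrt(1/29.6 + 1/360) = 0.191, so the 95% limits are a factor of exp(1.96 x 0.191) = 1.45 either way. With twice-Poisson variance, exp(1.96 x 0.191 x sqrt 2) = 1.70.
- At 3 per month: 88.8 against 1,080. SE = 0.110, factor 1.24 (1.36 with twice-Poisson variance).
- Per subject at the floor: mean 0.99 seizures, and exp(-0.99) = 37% of subjects would record none.

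The three assumed values of k correspond to mismatches by factors of 1/0.7 = 1.43, 1/0.9 = 1.11 and 1.20. At the floor all three lie within 1.45. At 3 per month only the first exceeds 1.24.

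**What the sensitivity analysis would look like.** Let R be the diary-to-retrospective ratio. Adjusted reduction = 1 - (1 - reported reduction)/R. If R were estimated at 1.0, a reported 50% reduction would span 1 - 0.5 x 1.45 = 28% to 1 - 0.5/1.45 = 66% at the floor, and 38% to 60% at 3 per month. A reported 90% reduction would span 86% to 93% at the floor.

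**The case against.** A reader might infer that every percent reduction sets pure recall against a diary and that the mismatch can never be checked. The documents do not support that. Appendix B admits an existing subject diary, entry rests on the medical record, and inclusion 2 requires seizures that can be reliably counted. Subjects with a prior diary could give a partial check if the source were recorded. What is true is that no check is planned.

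A reader might also infer that the seizure results as a whole are compromised. They are not. The seizure outcome with a stated time point of primary interest is Kaplan-Meier freedom from seizures with altered awareness at 24 months, which uses no baseline count. Engel I and ILAE 1 to 3 use none either. The exposed outcomes are secondary and descriptive, and the responder proportion and absolute rate change are optional analyses. No power or alpha figure changes. When reductions are large the distortion is small.

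The strongest objection is to the remedy. Thirty days is normally a maximum, so the diary may be shorter. Even if under-capture at k = 0.7 raised the diary count to 29.6/0.7 = 42.3, the SE would be sqrt(1/42.3 + 1/360) = 0.163, and the chance that the interval excludes 1 would be about 59% (0.357/0.163 = 2.19 against 1.96). Nor does the ratio isolate capture. Subjects are selected on the same 12-month count that supplies the baseline, so regression to the mean enters, and Appendix A permits periprocedural AED changes. Rev B's lack of a run-in may be a deliberate choice for a feasibility study.

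These points limit what the diary can do, and all of them stand. They do not remove the unchecked change of method or the conflict with the SAP.

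**Conclusion.** The point holds as a modest limitation that is cheap to improve. Rev B's baseline and follow-up counts come from different methods, and nothing planned tests whether they agree. The sign of any bias is unknown. Its size rests wholly on the assumed capture ratio: for ratios of 0.7 to 1.2 it runs from 21 points too low to 8 points too high at a true 50% reduction, and from 4 points too low to 2 points too high at a true 90% reduction.

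The mismatch between the two documents needs no assumption. The SAP calls for a prospective Baseline Phase that the current protocol does not collect, and this must be reconciled whether or not a pre-LITT diary is added.

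A reader might conclude that a 30-day diary could replace the retrospective baseline. The counts above rule that out: it is too sparse per subject and serves only as a group-level check.

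**What to change.** 1. In Protocol Table 1, Section 7.6.1 and Appendix B, dispense the diary at the Baseline visit (change T to T/D) and collect it on the day of LITT.
2. Record on the CRF the source of each retrospective baseline count: history, medical record or subject diary.
3. Keep the retrospective counts as the main baseline. Name that one baseline period in both Protocol Section 10.1.3 and SAP Section 11.1.3, replace the SAP's Baseline Phase wording, and bring SAP Table 1 into line. State which data, if any, will support the SAP's baseline seizure-free days and longest seizure-free interval.
4. Report the pooled diary-to-retrospective rate ratio with a 95% interval that allows for overdispersion and for variance in the retrospective counts, leaving out days with periprocedural AED changes. Show the percent reduction across that interval as a descriptive sensitivity analysis.
5. State the limits in the SAP: with about 30 diary days per subject, the ratio is known to a factor of about 1.45 at 1 seizure per month (1.7 with twice-Poisson variance) or about 1.24 at 3 per month. It can therefore show only large mismatches, it also reflects regression to the mean from selection on the retrospective count, and it cannot replace per-subject baselines.

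Cost: a small added diary burden for subjects, a minor CRF edit and a SAP revision that is needed in any case. Surgery is not delayed.

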APPENDIX C NEUROPSYCHOLOGICAL TESTING

This study will include a core neuropsychological battery as well as a supplementary battery.

The tests in the core battery were chosen based on the following criteria:

- 1) they are recommended by the National Institute of Neurological Disorders and Stroke (NINDS) as common data elements in studies of the neuropsychological effects of epilepsy and its treatments⁶,
- 2) they assess a broad range of cognitive domains that might plausibly be affected by a novel surgical approach or post-surgical complications,
- 3) they assess domains commonly affected by temporal lobe dysfunction,
- 4) the threshold for a statistically reliable decline have been defined in prior studies,^{7,8, 9, 10} and
- 5) valid analogue versions are available in Spanish.¹¹

The core battery does not include a test of non-verbal or visual memory because such measures are unlikely to be sensitive to LITT effects in the non-dominant temporal lobe, and verbal memory measures should be sufficiently sensitive to these effects. Despite occasional positive results in smaller, selected samples, larger studies and meta-analyses^{12, 13, 14} have failed to provide consistent evidence that standardized neuropsychological measures of visual memory are sensitive to non-dominant temporal dysfunction. Rates of statistically reliable changes (improvements and declines) on visual memory tests do not differ between dominant and non-dominant temporal lobe resections, suggesting that these tests are non-specific indicators of temporal lobe dysfunction. On the other hand, approximately 20% of patients show reliable declines after non-dominant temporal lobectomy on verbal memory tests.¹⁵

Minimally invasive neurosurgical approaches have the potential to reduce sub-acute cognitive morbidity associated with the trauma of craniotomy and extensive resection and allow for a more rapid return to full functioning. Therefore, we further recommend that a subset of cognitive domains that are dependent on temporal lobe dysfunction be assessed by a *supplementary* battery administered at the Baseline, Month 3, Month 6 and Month 12 visits. Assessment of cognitive outcomes is typically

⁶ https://commondataelements.ninds.nih.gov/epilepsy.aspx#tab=Data_Standards

The tests in the **supplementary battery** were chosen based on the following criteria:

- 1) they assess cognitive abilities (naming, verbal memory, semantic knowledge) that are known to depend on intact temporal lobe function;
- 2) multiple forms are available (or can be readily constructed from available stimuli) to minimize practice effects across visits; and
- 3) content does not overlap with tests in the core battery (to avoid enhancing practice effects on the core battery and maintain comparability of the core battery's results to prior studies that have relied on a single post-operative assessment).

NOTE: Validated versions of the supplementary battery are limited to the English language format, making the supplementary battery available only for subjects tested in English.

A brief description of all tests is outlined below. The test schedule for both English and Spanish-speaking subjects is provided in Table 5 and Table 6, respectively.

Core Battery – English-Speaking Subjects

Wechsler Adult Intelligence Scale-IV (WAIS-IV)

The WAIS-IV is a general test of intelligence developed to measure cognitive ability in adults. The WAIS can be administered in 60-90 minutes and yields a full-scale IQ (FSIQ), general ability index (GAI) and 4 index scores: verbal comprehension index (VCI), perceptual reasoning index (PRI), working memory index (WMI) and processing speed index (PSI).

Rey Auditory Verbal Learning Test (RAVLT)

The RAVLT is a verbal learning and memory test that consists of a list of 15 words which an examiner reads aloud at the rate of one per second. The subject's task is to repeat all the words he or she can remember, in any order. This procedure is carried out a total of five times. Then the examiner presents a second list of 15 words, allowing the subject only one attempt at recall. Immediately following this, the subject is asked to remember as many words as possible from the first list. This is followed by a yes/no recognition trial, where subjects are asked to distinguish the 15 original words from 15 distractor words. Completion time is estimated at 15 minutes.

Boston Naming Test-60 (BNT-60)

The 60-item BNT is a visual confrontation naming test sensitive to deficits in semantic retrieval. The BNT contains 60 line drawings graded in difficulty. Subjects are required to verbally name pictures (line drawings) of common objects. Items are rank ordered in terms of their ability to be named, which is correlated with their frequency. This test is appropriate for adults.

Controlled Oral Word Association Test (COWAT)

The COWAT uses the three letter set of F, A, and S to assess phonemic fluency. Individuals are given 1 minute to name as many words as possible beginning with one of the letters. The procedure is then repeated for the remaining two letters.

Animal Naming Test

The animal naming test is a category fluency test that measures impairment in verbal production, semantic memory and language. The subject is asked to verbally name as many animals as they can in a 60 second time period.

Trail Making Test

The test consists of two parts and requires a subject to 'connect-the-dots' of 25 consecutive targets on a sheet of paper or computer screen as fast as possible while still maintaining accuracy. If the subject makes an error, the test administrator is to correct them before the subject moves on to the next dot. The goal of the test is for the subject is to finish the part A and part B as quickly as possible. The time taken to complete the test is used as the primary performance metric. Part A is used primarily to examine cognitive processing speed. Part B is used to examine executive functioning.

Grooved Pegboard Test

The Grooved Pegboard is a manipulative dexterity test. This unit consists of 25 holes with randomly positioned slots. Pegs, which have a key along one side, must be rotated to match the hole before the peg can be inserted. This test requires more complex visual-motor coordination than most pegboards. Completion time is estimated at 20 minutes.

Supplementary Battery – English-Speaking Subjects Only

Logical Memory Test

This is a set of brief stories based on the Wechsler Memory Scale Logical Memory subtest developed specifically for use in studies using a repeated paradigm.¹⁸ Subjects are read a paragraph-length story at a rate of one idea per second. Following completion of the story, subjects are asked to repeat as much of that story as they can. Each word item recalled in 30 seconds scores two points for "immediate recall" regardless of the order of recall. The paragraph is read one more time and patients are asked to

¹⁸ Cunje A, Molloy DW, Standish TI, Lewis DL. Alternate forms of logical memory and verbal fluency tasks for repeated testing in early cognitive changes. *Int Psychogeriatr*. 2007;19(1):65-75.

remember the paragraph. After a delay period, subjects are asked to recall the paragraph once again, providing a “delayed recall” score. The estimated time for this test is five minutes.

Auditory Naming Test

A set of 15 test items will be drawn from the 50-item form developed by Hamberger, et al.¹⁹

The auditory naming test requires examinees to name concrete items described orally.

Visual Naming Test

A set of 15 test items will be drawn from the 50-item form developed by Hamberger, et al.¹⁹

Visual naming requires the naming of 30 line drawings or parts thereof (e.g., telephone, telephone dial).

Verbal Fluency Test

Versions of this test will be derived by the forms developed by Cunje et al¹⁸ specifically for use in studies using a repeated paradigm. In verbal fluency tests, participants have to say as many words as possible from a category in a given time (usually 60 seconds).

Table 5: Neuropsychological Testing Requirements for English-Speaking Subjects

Test		Baseline ¹	Month 3	Month 6	Month 12*	Early Withdrawal
CORE						
WAIS-IV		X			X	X
RAVLT		X			X	X
BNT-60		X			X	X
COWAT		X			X	X
Animal Naming		X			X	X
Trail Making		X			X	X
Grooved Pegboard		X			X	X
SUPPLEMENTARY						
Logical Memory		Form 1	Form 2	Form 3	Form 1	
Auditory Naming		Form 1	Form 2	Form 3	Form 1	
Visual Naming		Form 1	Form 2	Form 3	Form 1	
Verbal Fluency		Form 1	Form 2	Form 3	Form 1	

¹ Prior neuropsychological testing may be used for baseline values if the testing was conducted within 6 months prior to the baseline visit and there were no significant changes to the subject's AEDs or changes to the subject's clinical condition that may affect cognitive function.

Core Battery – Spanish-Speaking Subjects

Raven's Standard Progressive Matrices (SPM)™ Test

Raven's SPM is a test commonly used as a nonverbal means to estimate intelligence level in non-English speaking subjects. It will be used as an IQ estimate for Spanish-speaking subjects participating in this study. The test assesses observation skills and clear-thinking ability. It offers insight about someone's capacity to observe, solve problems, and learn. The test has a total of 60 items presented in 5 sets (A–E), with 12 items per set. The Raven's SPM produces a single raw score as well as percentile rank to indicate

¹⁹ Hamberger MJ, Seidel WT. Auditory and visual naming tests: normative and patient data for accuracy, response time, and tip-of-the-tongue. *J Int Neuropsychol Soc*. 2003;9(3):479-489.

the candidate's educative ability or the ability to think clearly and extract meaning out of events, compared to a norm group.

WHO-UCLA Auditory Verbal Learning Test (AVLT)

This is version of the RAVLT paradigm modified for non-English-speaking subjects. The Spanish translation will be used for Spanish-speaking subjects participating in this study. Like the RAVLT, it is a verbal learning and memory test that consisting of a list of 15 different words, which an examiner reads aloud at the rate of one per second. The subject's task is to repeat all the words he or she can remember, in any order. This procedure is carried out a total of five times. Then the examiner presents a second list of 15 words, allowing the subject only one attempt at recall. Immediately following this, the subject is asked to remember as many words as possible from the first list. This is followed by a yes/no recognition trial, where subjects are asked to distinguish the 15 original words from 15 distractor words. Completion time is estimated at 15 minutes.

Ponton-Satz Boston Naming Test (PS-BNT)

The PS-BNT is a modified version of the Boston Naming Test consisting of 30 items from the original BNT selected by experts on the basis of appropriateness for the use with Spanish speakers. As in the English version, subjects are required to verbally name pictures (line drawings) of common objects. Items are rank ordered in terms of their ability to be named, which is correlated with their frequency.

Controlled Oral Word Association Test (COWAT)

The COWAT uses the three letter set of F, A, and S to assess phonemic fluency. Individuals are given 1 minute to name as many words as possible beginning with one of the letters. The procedure is then repeated for the remaining two letters. (The procedure used for Spanish-speaking subjects is identical to the procedure used for English-speaking subjects.)

Animal Naming Test

The animal naming test is a category fluency test that measures impairment in verbal production, semantic memory and language. The subject is asked to verbally name as many animals as they can in a 60 second time period. (The procedure used for Spanish-speaking subjects is identical to the procedure used for English-speaking subjects.)

Color Trails Test

This is a version of the commonly used Trail Making Test, modified for use with non-English-speaking subjects. The Color Trails Test assesses sustained attention and divided attention in adults. Numbered circles are printed with vivid pink or yellow backgrounds that are perceptible to color-blind individuals. For Part 1, the respondent uses a pencil to rapidly connect circles numbered 1-25 in sequence. For Part 2, the respondent rapidly connects numbered circles in sequence, but alternates between pink and yellow. The length of time to complete each trial is recorded, along with qualitative features of performance indicative of brain dysfunction, such as near-misses, prompts, number sequence errors, and color sequence errors.

Grooved Pegboard Test

The Grooved Pegboard is a manipulative dexterity test. This unit consists of 25 holes with randomly positioned slots. Pegs, which have a key along one side, must be rotated to match the hole before the peg can be inserted. This test requires more complex visual-motor coordination than most pegboards. Completion time is estimated at 20 minutes. (The procedure used for Spanish-speaking subjects is identical to the procedure used for English-speaking subjects.)

Table 6: Neuropsychological Testing Requirements for Spanish-Speaking Subjects

Test		Baseline ¹	Month 3	Month 6	Month 12	Early Withdrawal
CORE						
Raven's Matrices		X			X	X
WHO-UCLA AVLT		X			X	X
Ponton-Satz BNT		X			X	X
COWAT		X			X	X
Animal Naming		X			X	X
Color Trails		X			X	X
Grooved Pegs		X			X	X

¹ Prior neuropsychological testing may be used for baseline values if the testing was conducted within 6 months prior to the specific baseline visit and there were no significant changes to the subject's AEDs or changes to the subject's clinical condition that may affect cognitive function.

